10.1.2 Unexpected adverse event

Any adverse event not reported in the safety section of the Investigator's Brochure or if the event is of greater frequency, specificity or severity.

10.1.3 Serious adverse event (SAE)

Any adverse event occurring that:

- Results in death
- Is a life threatening adverse experience defined as any adverse event that places the subject, in the view of the investigator, at immediate risk of death from the reaction as it occurred. Note that this does not include a reaction that had it occurred in a more severe form, it would have caused death.
- Results in subject hospitalisation or prolongation of existing hospitalisation.
- Subject becomes pregnant while on study drug

The following hospitalisations are not considered to be SAEs:

- Those planned before entry into the study
- Elective treatment for a condition unrelated to study indication or study treatment
- Occur on an emergency outpatient basis and do not result in admission (unless fulfilling other criteria in SAE definition)
- Part of normal treatment or monitoring of the study indication and are

not associated with any deterioration in condition.

- Results in a significant or persistent disability or incapacity defined as any event that results in a substantial and/or permanent disruption of the subject's ability to carry out normal life functions.
- Is any instance of overdose, either accidental or intentional (suspected or confirmed)
- Is any other important medical event, based upon appropriate medical judgement, that may jeopardise the subject or may require medical or surgical intervention to prevent or avert one of the outcomes listed above.

10.2 Detecting and documenting AE

Information about all AEs, whether volunteered by the patient, discovered by investigator questioning or detected through physical examination, laboratory test or other means, would be documented on the Adverse Event Form and followed up as appropriate. The AE form should be faxed to the coordinating investigator [name] [name] at [contact] and email [contact].

When eliciting experiences of AE from a subject, ask a standard non-leading question like "Do you feel different in any way since starting the new treatment/the last visit?" This question will be put to the subject in his/her own language at each study visit.

Each AE should be described by:

1. Nature of AE

This should be documented in terms of a medical diagnosis(es). When this is not possible, the AE should be documented in terms of signs and/or symptoms observed by the investigator or reported by the subject.

2. Duration

Start and end dates

3. Assessment of causality

The investigator should attempt to explain each AE and assess its

relationship, if any, to the study treatment. Causality should be assessed using the following definitions:

- Very likely
 - The AE follows a reasonable temporal sequence from study treatment administration
 - Abates upon discontinuation of study treatment
 - Reappears on repeated exposure (re-challenge)
- Probable
 - The AE follows a reasonable temporal sequence from study treatment administration
 - Abates upon discontinuation of study treatment
 - Cannot reasonably be explained by known characteristics of the subject's clinical state
- Possible
 - The AE follows a reasonable temporal sequence from study treatment administration
 - But could have been produced by the subject's clinical state or other mode of therapy administered to the subject
- Doubtful
 - The temporal association between study treatment and AE is such that the study treatment is not likely to have any reasonable association with the observed event
- Very unlikely
 - The AE is definitely produced by the subject's clinical state or other mode of therapy administered to the subject

The degree of certainty with which an AE is attributed to study treatment or alternative cause like natural history of disease or concomitant treatment should be guided by the following considerations:

- Time relationship between treatment and occurrence of AE
- De-challenge and re-challenge information, if applicable
- Known pharmacology of the drug
- Dose response relationships
- Lack of alternative explanations i.e. no concomitant drug used and no other inter-current disease

- Reaction of similar nature being previously observed with this drug or class of drug
- Reaction having often been reported in literature for similar drug

4. Severity of AE

- Mild: awareness of signs or symptoms, but they are easily tolerated
- Moderate: enough discomfort to cause interference with usual activity
- Severe: incapacitating, with inability to work or do usual activity.

Note that a severe AE is not necessarily serious. The term severe is a measure of the intensity while a serious AE is determined based on regulatory criteria. A life threatening AE is an SAE.

5. Final outcome

- Recovered/ resolved- The subject has fully recovered, or by medical or surgical treatment the condition has returned to the level observed at the first trial-related activity after the subject signed the informed consent
- Recovering/resolving- The condition is improving and the subject is expected to recover from the event. This term is only applicable if the subject has completed the trial or has died from another AE.
- Recovered/ resolved with sequelae- The subject has recovered from the condition, but with lasting effect due to a disease, injury, treatment or procedure. If a sequela meets an SAE criterion, the AE must be reported as SAE.
- Not recovered/not resolved- The condition of the subject has not improved and the symptoms are unchanged, or the outcome is not known.
- Fatal- This term is only applicable if the subject died from a condition related to the reported AE.
- Unknown- This term is only applicable if the subject is lost to followup

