6.2 Potential Benefits

Cholestyramine is a bile acid sequestrant that decreases the enterohepatic circulation of thyroid hormones in subjects with overt hyperthyroidism. Solomon, Kaykhaei, Mercado and Tsai et al. have all demonstrated that Cholestyramine is effective in reducing thyroid hormones with minimal side effects when added to standard therapy for up to 4 weeks of treatment. Although the common side effect is constipation, it may prove useful in hyperthyroid patients with hyperdefecation.

Prednisolone reduces the conversion of T_4 to T_3 in the circulation. Prednisolone 30 mg daily used short term effectively normalised thyroid hormone levels in 2 weeks in a series of 4 cases prior to subtotal thyroidectomy. No adverse reactions reported in this case series. In a similar study using betamethasone 0.5 mg 6 hourly coupled with iopanoic acid (500 mg 6 hourly) and propanolol for 5 days as preparation for hyperthyroid patients for surgery, drug tolerance was excellent with no serious side effects noted even in pregnant patients and no anesthetic incidents or post operative complications.

This study conducted with Cholestyramine or Prednisolone as adjunctive therapy is short term (4 weeks) and therefore minimise long term side effects of both drugs and minimise the risk of iatrogenic hypothyroidism. It has the potential to rapidly reduce thyroid hormones in a short span of time thus achieving euthyroidism promptly, improving thyrotoxic symptoms especially those with severe hyperthyroidism, the elderly and those complicated with fast atrial fibrillation and thyrotoxic cardiomyopathy. It may be useful in preoperative or pre radioactive iodine treatment where there is a need to achieve euthyroidism to prevent risks of thyrotoxic crisis. Prednisolone is readily available in most hospitals in Malaysia and fairly cheap.

This study will provide definitive efficacy and safety information of both

Cholestyramine and Prednisolone as adjunctive treatment in patients with overt hyperthyroidism. The overall benefits of this study outweigh the potential risks.

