9.9 Assessment of safety

Safety data will be analysed for the data collected throughout intervention period and up to follow up period. The following endpoints will be collected:

- Number of subjects with adverse effects during the intervention period and follow up period (total duration 6 weeks)
 - Subjects will be asked to report about adverse reactions (specified in the protocol) at 2 weeks, 4 weeks of intervention period and 2 weeks after end of study treatment period.
 - Number of subjects with serious adverse events during intervention period and follow up period (total duration 6 weeks)
 - Subjects will be asked to report about SAE immediately during the intervention period and follow up period

Safety and tolerability assessments will consist of:

- Regular performance of physical examinations
 - 1. BP, PR, Temperature, Weight (kg)
- Regular monitoring of laboratory tests
 - FPG/ RPG, Electrolytes (Na⁺, K⁺, Urea, Creatinine), FT₄, FT₃, TSH
- Monitoring and recording all adverse reactions and serious adverse events

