10 ADVERSE EVENTS

10.1 Definitions

10.1.1 Adverse event (AE)

Any untoward medical occurrence in a subject administered an investigational product and which does not necessarily have a causal relationship with treatment.

An AE includes:

- 1. A clinically significant worsening of a concomitant illness
- 2. A clinical laboratory adverse event: a clinical laboratory abnormality which is clinically significant, i.e an abnormality that suggests a disease and/or organ toxicity and is of a severity active management, Active that requires management includes active treatment or further investigations, for example change of medicine dose or more frequent follow-up due to the abnormality.

The following should be reported as AE:

Treatment of emergent symptoms which include:

- Medical conditions or signs or symptoms that was absent before starting study treatment.
- In this trial the following events must be collected and reported:
 - 1. SAEs
 - 2. AEs leading to discontinuation of study drug
 - 3. Gastrointestinal symptoms
 - a. Constipation
 - b. Bloating
 - c. Diarrhea
 - d. Abdominal pain
 - e. Vomiting
 - 4. Diabetes
 - 5. Hypokalemia
 - 6. Hypothyroid

- The following abnormal laboratory values particularly to this study will be observed
 - Fasting plasma glucose more ≥7 mmol/L or Random plasma glucose ≥ 11.1 mmol/L
 - Serum K+ <3.5mmol/L
 - TSH above upper limit of reference range and FT₄ normal or below lower limit of reference range
- Any doubtful event should be treated as an AE.

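### The plan does not say how prompted and open questions about adverse events combine, and it schedules no structured symptom record before treatment, so its rule on pre-existing symptoms cannot be applied consistently

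*Combined protocol and SAP*

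**What the plan says.** **How events are asked for.** Protocol section 9.9 states: "Subjects will be asked to report about adverse reactions (specified in the protocol) at 2 weeks, 4 weeks of intervention period", and again two weeks after treatment ends. Section 10.2 states: "When eliciting experiences of AE from a subject, ask a standard non-leading question". It gives an example that asks whether the subject feels different since starting the new treatment or since the last visit, and adds: "This question will be put to the subject in his/her own language at each study visit". The same section accepts events "whether volunteered by the patient, discovered by investigator questioning or detected through physical examination", or by laboratory test.

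**What counts.** Section 10.1.1 lists as emergent: "Medical conditions or signs or symptoms that was absent before starting study treatment". It also counts as an adverse event: "A clinically significant worsening of a concomitant illness". It names five gastrointestinal symptoms that must be collected: constipation, bloating, diarrhoea, abdominal pain and vomiting. The glossary (section 4) defines constipation as fewer than three bowel movements a week, and diarrhoea as three or more loose stools a day with abrupt onset. For final outcome, section 10.2 measures recovery against the level at the first trial-related activity after consent.

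**What is recorded before treatment.** Section 11.1.1 lists hyperthyroid, past medical, cardiovascular, family, smoking and medication history, and an examination. Section 11.1.2 repeats history and examination only if they were not done at screening. The activities table marks adverse event reporting at Visits 3, 4 and 5.

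**How the counts are used.** Section 9.9 makes the number of subjects with adverse effects over six weeks a safety endpoint. Section 13.2.2 compares proportions by chi-square test. Safety is the only secondary objective (section 7.2), and the trial is open label.

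**The concern.** Spontaneous and prompted reporting generally give different event rates. Here both are prescribed, with no order, no fixed list of prompts and no rule for which reports enter the endpoint. Staff at three sites know the allocation. One investigator may probe for constipation in Group 1 while another asks only the open question in Group 3, and both would be following the protocol.

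The second gap is the baseline. Deciding whether a symptom is new, worse or resolved needs its pre-treatment level, and an analyst cannot recreate that level after dosing. The patient group makes this more than a formality. Section 6.2 says of cholestyramine and its constipating effect that "it may prove useful in hyperthyroid patients with hyperdefecation", so the plan itself expects some patients to enter with altered bowel habit and expects one study drug to change it.

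At stake is the between-arm comparison of gastrointestinal events. Section 6.2 promises definitive safety information on both adjuncts.

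**Working it through.** **1. Setting the rules beside the schedule**

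| What the plan's rules need | What the body text schedules |
|---|---|
| Symptom absent before treatment (10.1.1) | General history at Visit 1, or at Visit 2 if missed; no listed-symptom item |
| Worsening of a concomitant illness (10.1.1) | No pre-treatment severity or frequency of the listed symptoms |
| Recovery to the level at the first trial activity (10.2) | No structured record of that level |
| Weekly or daily stool frequency (section 4) | No stool count; the diary card is described only for adherence (9.6) |

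The open question is assigned to every study visit, which could literally include baseline, but a question about change since treatment began or since the last visit does not fit there. The two bowel definitions are also unequal. Diarrhoea needs abrupt onset, so chronic frequent stools should not meet it. Constipation is a bare frequency threshold with no onset or change condition, so a patient who had it before treatment still meets it at week 2.

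**2. Is there a figure in the plan to reproduce?** There is none for adverse events: section 13.1 bases the sample size on the primary objectives only. The efficacy figure is sound enough to take 45 per arm as given. For 40% versus 70%, two-sided pooled Z test, alpha 0.05, the normal approximation gives 41.97, so 42 per arm. Exact binomial power is 0.796 at 40 and 0.813 at 41, against the stated 41. Dropout: 41 / 0.9 = 45.6, against the stated 45.

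**3. Illustration of equal miscounting.** Every rate below is an assumption. Let e be the rate of new events and q the share of each arm with a pre-existing symptom that is wrongly counted. The observed rate is q + (1 − q)e, so the arm difference shrinks by the factor (1 − q). Take e = 5% versus 20%, 45 per arm, and exact enumeration of the two-sided pooled Z test, which for two arms is the chi-square test without continuity correction.

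| q | Observed rates | Difference | Power |
|---|---|---|---|
| 0 | 5.0% v 20.0% | 15.0 points | 63% |
| 5% | 9.75% v 24.0% | 14.25 points | 46% |
| 10% | 14.5% v 28.0% | 13.5 points | 36% |
| 20% | 24.0% v 36.0% | 12.0 points | 25% |
| 30% | 33.5% v 44.0% | 10.5 points | 17% |

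The 5% row also describes a 20% baseline prevalence of which only a quarter is miscounted (0.20 × 0.25 = 0.05). With 5% versus 30%, power is 92% at q = 0 and 53% at q = 20%.

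**4. Illustration of unequal miscounting.** Suppose new events are 5% in both arms, so the true difference is zero. If q is 10% in one arm only, because staff probe there and not elsewhere, that arm shows 0.10 + 0.90 × 0.05 = 14.5% against 5%, a false difference of 9.5 points against whichever arm was probed. If instead 20% have a pre-existing symptom that is counted, and the resin relieves half of it in Group 1, Group 3 shows 0.20 + 0.80 × 0.05 = 24% and Group 1 shows 0.10 + 0.90 × 0.05 = 14.5%. That is an apparent benefit with no difference in new events.

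**The case against.** The strongest reply is that the plan already intends the right thing. An open question followed by directed questions is ordinary practice, and section 10.2 expressly admits events found by investigator questioning. Section 10.1.1 limits emergent symptoms to those absent before treatment. The open question asks about change, each event needs a start date, and diarrhoea needs abrupt onset. Medical and hyperthyroid history is taken before dosing. The example question already offers the since-last-visit wording. The appendix list in section 16 includes study procedures and a CRF that are not shown and might hold a symptom checklist.

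Most of this stands, and it rules out two stronger readings. A reader might infer that the two methods contradict each other. They do not; what is missing is the order and the rule for which source feeds the endpoint. A reader might also infer that pre-existing thyrotoxic bowel symptoms are counted as adverse events and dilute the drug effects. The plan's rules exclude them, so miscounting is a risk and not a prescribed outcome. Dilution in particular assumes equal error in every arm, which an open-label trial does not guarantee.

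What the reply does not supply is a means of applying those rules. A start date recalled at week 2 is a weaker basis than a record made before the first dose. A general history with no bowel item may or may not mention the symptom. An unseen CRF page could help, but the body text and activities table should then refer to it.

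**Conclusion.** The concern holds in a limited form. The plan leaves two gaps: no rule for combining prompted and open elicitation, and no scheduled structured record of the listed symptoms before treatment. Together they prevent consistent application of the plan's own exclusion of pre-existing symptoms, of its worsening rule and of its recovery reference. Constipation is the most exposed event, because its definition carries no change condition.

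The direction of any bias is not determined, and its size cannot be derived from the documents, which give no prevalence of baseline bowel symptoms and no expected event rates. The fall in power from 63% to between 17% and 46% rests on assumed rates of 5% and 20%, an assumed miscounted share of 5% to 30%, and equal error in all arms. It shows that the mechanism could matter, for a comparison that was not powered in the first place. It is not an estimate of what will happen. The primary efficacy analysis is unaffected. This is a cheap improvement and not a fatal fault.

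**What to change.** Use one procedure in all three arms and write it into sections 9.9 and 10.2 and the activities table:

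- At Visits 3, 4 and 5, ask the open question first, worded only as since the last visit, then complete a fixed checklist of the protocol-listed symptoms with stool frequency.
- Complete the same checklist at Visit 2, before randomisation and the first dose. Baseline assessment and randomisation already fall on the same day (section 11.1.2), so the record can be made before anyone knows the allocation.
- Count a listed symptom as an adverse event only if it is new or worse than the Visit 2 record, and state that this count feeds the safety endpoint.
- Tabulate solicited and unsolicited events separately by arm.

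The cost is a one-page CRF checklist at four existing visits and a few minutes each time. Prompting will raise absolute event rates in every arm, which makes comparison with spontaneously reported rates elsewhere harder; the separate tabulation limits that. No treatment, visit or sample size changes.

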10.3 Reporting SAE

Information about all SAE will be documented in the AE form and reported to Coordinating Investigator of the study – [name] [name] ([contact], email: [contact]) and MREC directly within 24 hours.

10.4 Treatment and follow up of AE

Treatment of any AE is at the sole discretion of the investigator who should follow up subjects with AE until the event has resolved or until the condition has stabilised. Otherwise appropriate medical care should be arranged for the patient. Abnormal tests should be repeated until they return to baseline levels or an adequate explanation of the abnormality has been found.

- 1. Treatment of over-dosage significant enough to cause adverse effects
 - Study medication must be stopped immediately and subject be monitored closely for all adverse reactions. Immediate thyroid function test to be sent and reviewed.
- 2. Pregnancy
 - A female subject must be instructed to stop taking study medication and immediately inform the investigator if she becomes pregnant during the study. The investigator should counsel the subject and discuss the risks of continuing with the pregnancy and the possible effects on the foetus. Monitoring of the subject should continue until conclusion of the pregnancy. The investigator should report all pregnancies to the coordinating investigator and MREC within 24 hours of being notified of the pregnancy.
 - Pregnancy occurring in the partner of a subject participating in the study should also be reported to the investigator and sponsor. The partner should be counseled and followed as described above.
 Pregnancies will be formally reported as SAEs.
- 3. Hypokalemia
 - If mild hypokalemia (3-3.5 mmol/L), to replace with Mist Potassium Chloride and reassess K⁺ levels after 3 days. If moderate to severe hypokalemia (<3 mmol/L), to assess for symptoms and consider admission for close monitoring, ECG and oral/IV potassium replacement. To consider withdrawing treatment (especially prednisolone) if refractory to active intervention.

- 4. Diabetes
 - To reconfirm by sending a repeat FPG and 2 hour post prandial glucose. Upon confirming diagnosis of diabetes, consider starting oral hypoglycemic drugs. Consider discontinuing study treatment if severe uncontrolled hyperglycemia or hospitalisation for hyperglycemic emergencies.
- 5. Hypothyroid
 - Hypothyroid is defined as symptoms of hypothyroidism coupled with elevated TSH more 4.7mU/L and normal or low levels of Free T4 <9 pmol/L measured during intervention with study drug
 - If hypothyroidism occurs during study treatment, stop study treatment and repeat thyroid function test one week later. Thyroid function tests will be reviewed and medication adjusted. All adjustment to medications will be documented in CRF. No thyroxine will be given as hypothyroid will recover upon discontinuing study treatment. Subject will discontinue study treatment if develop persistent and severe profound symptoms of hypothyroidism
- 6. Hyperthyroid and thyroid storm
 - If subjects are still hyperthyroid (no reduction in Free T4 and Free T4 from baseline) at the end of week 4, Carbimazole will be increased in accordance to the standard practice. In the event if subjects are symptomatic of thyrotoxicosis throughout trial period, propanolol doses may be increased as per clinician judgement and documented in CRF. In the event that subject develops thyroid storm during trial period, SAE will be reported, study treatment discontinued and treatment of thyroid storm with lugol's iodine, beta blockers, hydrocortisone and high doses of propylthiouracil will be initiated as per standard practice.

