4 GLOSSARY OF TERMS

Eligible	Qualified for enrolment into the study based on strict		
	adherence to inclusion and exclusion criteria		
Investigator	Treating physician		
Subject(s)	Individuals enrolled in the clinical study		
Diabetes	Fasting plasma glucose more ≥7 mmol/L or Random plasma glucose ≥ 11.1 mmol/L		
Hypokalemia	Serum potassium (K⁺) <3.5mmol/L		
New onset sepsis	Defined as new onset life-threatening organ dysfunction caused by a dysregulated host response to infection.		
Hypothyroid	Symptoms of hypothyroidism coupled with biochemical Free T_4 normal or below lower limit of reference range and TSH above upper limit of reference range		
Drug	An immune mediated reaction to a drug and manifests as		
hypersensitivity Reaction	mild to severe skin rash, anaphylaxis or serum sickness		
Hospitalisation	An event that results in an admission to the hospital for		
	any length of time or prolongs the subject's hospital stay.		
	This does not include an emergency room visit or		
	admission to an outpatient facility		
All-cause mortality	An event that results in death of a subject		
Constipation	Fewer than 3 bowel movements a week		
Diarrhea	Abrupt onset of 3 or more loose stools per day		

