6.1 Potential Risks

Cholestyramine is a bile acid sequestrant that works by increasing the removal of bile acids from the body. The most common adverse reaction is constipation but most instances are mild, transient and controlled with conventional therapy. Other less frequent adverse reactions are abdominal discomfort, flatulence, nausea, vomiting and bleeding tendencies due to hypoprothrombinemia if use long term. Detailed information can be found on the drug leaflet attached at the appendix. Solomon et al. reported all patients tolerated cholestyramine without inordinate difficulty with 2 patients experienced hyperdefecation for a couple of days and all patients complained of the taste of the powders¹¹.

Prednisolone is a corticosteroid and work by modifying the body's immune to various conditions and decreasing inflammation. response In hyperthyroidism it reduces the conversion of T_4 to T_3 . The common adverse reactions include fluid retention, alteration in glucose tolerance, elevation in blood pressure, behavioural and mood changes, increased appetite and weight gain. There is a risk of hypothalamic-pituitary-adrenal axis suppresion and Cushing's syndrome if given long term. It may increase the risks related to infection but rate of occurrence increases with the dose of steroids. There may be an increase risk of peptic ulcer disease. If used long term may decrease bone density. In a meta analysis, the use of prednisone 35 mg daily for a mean 64 days increased the risk for diabetes (OR 1.7 (1.1-2.6) P= 0.02), hypertension (OR 2.2 (1.4-3.8) P =0.01), dermatologic effects (OR 4.5 (3.5-5.7) P= 0.001) but was not statistically significant association for peptic ulcer, bacterial sepsis, osteoporosis, psychosis and tuberculosis¹⁹. Steroids may cause muscle weakness from renal potassium loss and myopathy if taken long term but there are case reports of thyrotoxic periodic paralysis soon after glucocorticoid administration²². The detailed information regarding risks and adverse reactions to prednisolone can be found in the drug leaflet attached in the appendix.

The immediate risks foreseeable in this study would be the risk of iatrogenic hypothyroidism. However this risk is closely monitored and the event of

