8.4.1 Inclusion criteria

- 1. Provision of written consent by subject or guardian.
- 2. Subject of either sex, more than 18 years of age
- 3. Subjects with moderate to severe overt hyperthyroidism (caused by Graves' disease).
 - Moderate to severe overt hyperthyroidism is defined as Free T₄>
 1.5 times upper limit of normal reference range and TSH below lower limit of reference range, who are either newly diagnosed or previously diagnosed and receiving ATDs currently.
 - •Graves disease is defined as hyperthyroidism coupled with clinical signs of symmetrical diffuse goiter, thyroid orbitopathy, or diffuse and vascular thyroid on ultrasound or positive TRAb antibody.
- 4. Female patients will either be
 - post-menopausal for > 2 years
 - Women of childbearing potential can be included if surgically sterile or using double contraception with at least one method being barrier contraception. Women of childbearing potential must have a negative pregnancy test at screening and at randomisation. Pregnancy tests will be repeated during each visit.

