8.4.3 Subject withdrawal & drop-out

Subjects are free to withdraw from the study at any time for any reason. Subjects may also be withdrawn from the study at any time at the discretion of the investigator. The following are anticipated conditions/events that would require a subject to be withdrawn from the study:

- Adverse reactions or intolerance to study drug
- Protocol violation
- Subject requires use of unacceptable concomitant medication

- Subject not compliant with protocol procedures
- Subject develops a condition during the study that violates the inclusion/exclusion criteria
- Lost to follow-up
- Administrative problems
- Death

8.4.4 **Procedures for handling withdrawal**

Subjects who withdraw or are withdrawn from the study should:

- Have the reason(s) for their withdrawal recorded
- Be asked about the presence of any AEs and if so should be followed up by regular scheduled visits, telephone contact, correspondence or home visits until satisfactory clinical resolution of AEs is achieved.
- Be seen by an investigator and all final assessments will be performed and recorded in the OFF STUDY form.
- Be encouraged to continue coming for regular visits and assessments
- Have at least one follow-up contact (scheduled visit, telephone contact, correspondence or home visit) for safety evaluation during the 30 days following the last dose of study treatment.
- In the event of pregnancy, the subject should be monitored until conclusion of the pregnancy and the outcome of pregnancy reported.
- Have study treatment returned.

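### Every hypothyroid definition needs a raised TSH, so FT4 below 9 pmol/L with TSH not raised and mild or moderate symptoms triggers no hypothyroid-specific stop

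*Combined protocol and SAP*

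**What the plan says.** Four places in the combined protocol and SAP define hypothyroid, and all four depend on TSH:

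- **Glossary (section 4):** symptoms, with FT4 "normal or below lower limit of reference range and TSH above upper limit of reference range".
- **Section 10.1.1, laboratory values to be observed:** "TSH above upper limit of reference range and FT₄ normal or below lower limit of reference range". No symptoms are needed here.
- **Section 10.4 item 5, which sets the action:** symptoms with "elevated TSH more 4.7mU/L and normal or low levels of Free T4 <9 pmol/L measured during intervention with study drug".
- **Section 11.2 item 4, a criterion for stopping treatment:** the same combination of symptoms, TSH above 4.7 mU/L and the FT4 wording of 10.4.

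At entry, 8.4.1 requires FT4 above 1.5 times the upper limit together with "TSH below lower limit of reference range, who are either newly diagnosed or previously diagnosed and receiving ATDs currently".

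On a defined case, 10.4 item 5 stops study treatment, repeats the thyroid tests a week later and adjusts medication. It rules out thyroxine because recovery is expected once study treatment stops. The same bullet ends with a sentence that discontinues study treatment for persistent and severe symptoms of hypothyroidism, and that sentence names no TSH or FT4 value.

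On the risk itself, section 6.1 states: "The immediate risks foreseeable in this study would be the risk of iatrogenic hypothyroidism".

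**The concern.** The protocol calls iatrogenic hypothyroidism the immediate foreseeable risk, and the week 6 visit exists partly to look for it. Because thyroxine is excluded, stopping or adjusting treatment is the remedy, and the rule that triggers the stop is the main safeguard specific to this event.

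That trigger depends on a marker that starts at the opposite end of its range in every subject. A subject whose FT4 has fallen below the reference range, and who has symptoms, is not a hypothyroid case under any of the four definitions unless TSH has also risen past its upper limit. What happens to that subject is then left to the individual investigator in an open-label trial, and the event may be labelled differently from one arm to another.

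**Working it through.** The plan states no figure on this point, so there is none to reproduce. The check is a logic table with two short calculations for scale.

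**Inputs.** Central-laboratory ranges from 11.4: FT4 9–25 pmol/L, TSH 0.4–4.7 mU/L. Entry limits from 8.4.1. Definitions from the glossary, 10.1.1, 10.4 item 5 and 11.2 item 4. Planned size 135 subjects. Central FT4 measured after baseline at weeks 2, 4 and 6 (11.1.4, 11.1.5).

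**Step 1: distance from entry.** This applies the central ranges to the entry limits, which is an assumption because screening tests are run at site laboratories.

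- FT4 at entry is above 1.5 × 25 = 37.5 pmol/L. Reaching 9 pmol/L is a fall of 1 − 9/37.5 = 0.76, so FT4 below 9 is a fall of more than 76%.
- TSH at entry is below 0.4 mU/L. To count, it must pass 4.7 mU/L, which is more than 4.7/0.4 = 11.75 times the entry limit.

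**Step 2: logic table at FT4 = 7 pmol/L.** The last sentence of 10.4 item 5 is read two ways: as standing alone, and as applying only within a defined case.

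| Symptoms | TSH (mU/L) | Glossary | 10.1.1 laboratory | 10.4 / 11.2 | Last sentence, standing alone | Last sentence, defined case only |
|---|---|---|---|---|---|---|
| None | 3.0 | No | No | No | No | No |
| Mild or moderate | 3.0 | No | No | No | No | No |
| Persistent, severe | 3.0 | No | No | No | Yes | No |
| None | 6.0 | No | Yes | No | No | No |
| Mild or moderate | 6.0 | Yes | Yes | Yes | No | No |
| Persistent, severe | 6.0 | Yes | Yes | Yes | Yes | Yes |

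The second row is the gap, and it is the same on both readings. The third row depends on the reading.

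**Step 3: does FT4 matter when TSH is not raised?** Repeating the TSH 3.0 rows with FT4 = 15 pmol/L gives identical answers. While TSH is not raised, a low FT4 changes nothing under any hypothyroid-specific rule.

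**Step 4: how far the last sentence reaches.** Section 10.2 defines severe as incapacitating. Mild and moderate symptoms therefore fall outside the sentence however it is read.

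**Step 5: frequency.** The documents do not say how often FT4 falls below 9 with TSH not raised, nor how TSH behaves on treatment. For scale only, each 1% of 135 subjects is 0.01 × 135 = 1.35 subjects.

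**Step 6: data already available.** 135 subjects × 3 visits = at most 405 central FT4 values.

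**The case against.** The strongest reply is that these subjects are not unprotected. New symptoms are adverse events under 10.1.1, as is a laboratory abnormality that needs a dose change, and doubtful events are to be treated as adverse events. Section 10.4 says "Treatment of any AE is at the sole discretion of the investigator" and also that "Abnormal tests should be repeated until they return to baseline levels or an adequate explanation of the abnormality has been found". Section 8.4.3 lists "Adverse reactions or intolerance to study drug" as a reason for withdrawal, and 11.2 stops treatment for intolerable reactions. All of this stands. It leaves the decision to judgement where a specific rule was evidently intended, but it keeps the point minor.

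The pattern may also be uncommon. Section 6 says antithyroid drugs mostly take 6 to 8 weeks to reach euthyroidism, and 13.1 assumes only 40% of Group 3 reach normal FT4. This stands as a reason not to assume a high frequency. It does not settle the matter, because 13.1 is sized to detect a 30-point higher proportion in the two adjunct arms and 6.1 itself gives prominence to the risk.

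A reader might infer three stronger things that the documents do not support:

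- **That no hypothyroid-specific rule can ever stop a subject whose TSH is not raised.** The last sentence of 10.4 item 5 names no TSH value and, taken literally, does so for persistent and severe symptoms. It sits in the bullet that opens on hypothyroidism having occurred, so its scope is unclear, but it cannot be ignored.
- **That such events drop out of the safety endpoint.** Section 9.9 counts subjects with any adverse effect and subjects with serious adverse events. The plan specifies no by-arm hypothyroid count to be biased, so the loss is one of labelling.
- **That 10.4 and 11.2 conflict in substance on restarting, or on the FT4 limit.** Section 11.2 reads naturally as no restart. The glossary, 10.1.1 and the range in 11.4 settle that 9 pmol/L marks low FT4.

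**Conclusion.** The concern holds in a limited form. All four definitions require a raised TSH in a population that enters with TSH below the lower limit. FT4 below 9 pmol/L with TSH not raised and mild or moderate symptoms meets none of them and triggers no hypothyroid-specific stop. With persistent and severe symptoms the answer turns on an ambiguous sentence.

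This follows from the text alone and needs no assumption about how TSH responds. The number of subjects affected cannot be derived from the documents, and the more-than-76% fall in FT4 assumes the central range at entry. No effect on the primary endpoint is shown. This is a minor point: a cheap improvement to a safety rule, not a flaw that threatens the trial's conclusions.

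**What to change.** 1. In 10.4 item 5 and 11.2 item 4, apply the stop and the one-week retest to symptomatic FT4 below 9 pmol/L whatever the TSH, subject to the clinical team's agreement.
2. In the safety analysis, tabulate by arm the subjects with central-laboratory FT4 below 9 pmol/L at weeks 2, 4 and 6 whatever the TSH, beside the hypothyroid adverse events.
3. While editing, and as clarification only, say whether study treatment may restart after the retest, and write the FT4 limb as normal, or low (below 9 pmol/L).

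**Cost.** Wording in two sections and one table built from values already scheduled. The only new blood draw is the one-week retest in each subject stopped, and the sample size does not change.

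**Downside.** Some subjects may have treatment interrupted before the week 4 endpoint. One stopped at the week 2 visit could lose up to 4 − 2 = 2 of the 4 treatment weeks. They remain in the intention-to-treat analysis. The reported number with low FT4 may also rise, because it will be looked for directly.
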